Design, Treatment Phase and Treatment Arms: This is a double-blind randomized group design, which will enroll 100 participants. After screening and baseline procedures, participants will be randomized to active or sham rTMS conditions (50 active, 50 sham); thus participants will have a 50% probability of receiving active treatment. Participants will receive 20 iTBS-TMS sessions over the course of 2 weeks. Participants will be required to be abstinent from alcohol and illicit substances for 5 days and demonstrate no clinically significant withdrawal symptoms prior to the first iTBS-TMS session.

Rationale for Brain Region Site: The left dorsolateral prefrontal cortex (DLPFC) was chosen as the rTMS stimulation site given excitatory transcranial magnetic stimulation to this region has been demonstrated to decrease cravings in non-Veterans with AUD. Additional stimulation of this site has been robustly shown to be associated with decreased unipolar depressive symptomatology; depressive disorders are highly comorbid in Veterans with AUD.

Duration of Treatment Phase: Active iTBS-TMS Treatment Group – will receive a total of 20 treatments delivered 5-6 days/week. Participants will typically receive two treatments per day (Monday-Friday), over 2 consecutive weeks; inter-treatment interval will be at least 2 hours. However, in the event the participant is unable to complete the typical two iTBS-TMS sessions per day due to participant or research personnel illness, scheduling issues, or other unforeseen circumstances. There have been no adverse events reported in the literature implementing multiple iTBS sessions per day in any population. Sham Treatment group will receive the same frequency and duration of treatment, without actual administration of iTBS-TMS. For both the active and sham iTBS-TMS groups, sessions will typically be conducted prior to the beginning of the participants treatment day, and at lunch, as to not interfere with their treatment-as-usual in the VA substance treatment clinics.

Procedures for Delivery of rTMS Sessions:

1. Anatomical localization of the left DLPFC for the stimulation coil will be individualized for each participant and achieved through standardized procedures for EEG electrode placement, optimized for transcranial magnetic stimulation.

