The iTBS-TMS operator will monitor all participants for ear protection, coil placement, and seizure activity during all sessions. All participants will be required to have abstained from alcohol or non-prescribed medication for 5 consecutive days prior to the first rTMS session. Prior to the first iTBS-TMS session, participants will be administered the Clinical Institute Withdrawal Assessment for Alcohol-Revised and must score < 8; scores > 8 are indicative of potential autonomic instability); participants with a score > 8 will immediately be escorted to their VAPAHCs Addiction Treatment Services clinic for further evaluation. Participants will be randomly screened x6 for alcohol (breath alcohol) and substance use (urine toxicology) prior to rTMS sessions during the 2 week treatment phase. If a participant's test positive or report any alcohol or substance use during the 2 week rTMS treatment period, they will be immediately withdrawn from the study. Additionally, prior to each participants will complete a rTMS screen, including inquiring about any changes in medications or comorbid medical conditions, amount of sleep, and suicide screening questionnaire prior to each rTMS session to assess for current suicide risk. Although patients in the study are regularly screened for alcohol and substance use and suicide risk while in treatment, we will conduct random alcohol/substance screening and pre-rTMS session suicide risk assessment to ensure participant welfare. Should a headache or site discomfort occur, these symptoms usually readily respond to acetaminophen or ibuprofen. Any reported pain typically improves over time or completely remits. To protect against possible hearing damage, participants will wear ear protection during rTMS sessions (foam ear plugs and noise attenuating headphones). This will greatly reduce the possibility of hearing loss. Hearing acuity testing pre-and-post rTMS is no longer a standard practice, given the remote likelihood of rTMS-related hearing loss.

Additional Procedures for the Monitoring of Seizures and Suicidal Ideation/Behavior:

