Screening, Baseline and Treatment Phase: In the unlikely event that a seizure does occur, participants will be closely monitored and treated for any medical or psychological consequences. rTMS sessions will be conducted at the VAPAHCs MIRECC, which fully equipped to safely handle a seizure. If at any point during study participation, a participant has a seizure, the participant will be withdrawn from the study immediately although they will still be followed for protocol assessments. All seizures will be considered serious adverse events (SAE) and as such, will be reported to the study PI. We will immediately suspend enrollment if 10 participants experience a seizure during study participation, and request that the Data Monitoring Safety Board (DMSB) evaluate the SAE data, to determine if enrollment of new participants should be resumed without protocol changes, if protocol modifications should be made before resuming enrollment, or if the study should be terminated. We recognize that study termination or modification based on SAEs, such as seizures, ultimately rests with the DMSB and the study PI. If a participant expresses suicidal ideation/intent, and is determined to be a risk to self, a clinical evaluation will be immediately conducted by the PI (a licensed clinical psychologist), Co-Is (board certified psychiatrists) or by the participant's individual mental health provider, and/or a mental health emergency clinician. The participant will remain with qualified study personnel or a MIRECC clinician until the evaluation has been completed and a decision made about disposition in conjunction with the Chief of Mental Health Outpatient Clinic or the emergency mental health clinician.

Follow-up Phase: If a participant discloses active suicidal or homicidal ideation or other clinically significant psychiatric symptomatology during the follow-up phase of the study, they will be provided with the

Title : Transcranial Magnetic Stimulation for the Treatment of Veterans With Alcohol Use Disorders
Approval Period: 02/28/2025 - 02/28/2026

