number and encouraged to call Veterans Crisis Hotline or present to a local hospital emergency department. In the event of a seizure (or other medical issues possibly secondary to rTMS, the participant will be requested to immediate contact their primary health care provider. In the event of disclosure of the above psychiatric emergencies or a seizure, the PI or psychiatrist Co-Investigator will also be immediately notified and will contact the participant for further assessment and determine the appropriate intervention. If a participant discloses that they relapsed during the follow-up period, they will be encouraged to recontact VAPAHCS Addiction Treatment Services for re-evaluation and possible re-engagement in treatment.

Magnetic Resonance (MR)Studies: Participants will be informed of risks, using the text provided and required by Stanford University's Institutional Review Board the VA. Our Research Assistants (RA) have been trained by the PI, CO-Is carefully pre-screen each participant for MRI safety before the MRI appointment. RA also have been certified to independently operate the CNI magnetic resonance scanner by qualified CNI personnel. Minimal risks are associated with MR scanning and 3T MR scanners are now routinely used in clinical practice. Study participants who have metal implants, cardiac pacemakers, metal fragments or a known tendency for claustrophobia will not be admitted to the study. Study participants will be scanned with a metal detector before entering the 3T scanner room, and all metal objects will be removed. There is a remote possibility that the magnet will attract a metal object, producing physical injury. To make certain

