Expedited Reporting by the Sponsor to the FDA: PI will review the SAE report to assess completeness of documentation and to determine whether the SAE requires expedited reporting to the FDA. Specifically, if an event meets the criteria for unexpectedness (i.e., not previously reported) and seriousness it will be reported as required by regulation to the FDA within 10 working days for UADEs and within 7 calendar days for unexpected SAEs (Safety Reports) of the sponsor receiving the report as required by regulation.

Data Monitoring Safety Board (DMSB): Reporting of Adverse Events, Adverse Device Effects, Serious Adverse Events, and Unanticipated Adverse Device Effects. Study Personnel will generate tabulations of AEs and SAEs and present a summary of these to the DMSB on a schedule set by the DMSB. The DMSB will also determine when they should be unblinded to treatment assignment for the reviewing of adverse event data. The DMSB will advise the PI concerning whether the study should continue or be stopped for safety

reasons. Communication among the Investigative Team: The PI will have a weekly group lab meeting with all RAs, and there will be a monthly lab meeting with all Co-Is and consultants some via Skype.

Additionally, the VAPAHCs MIRECC has weekly PI meetings to discuss issues relevant to ongoing MIRECC research projects. All key VA Co-Is associated with this project attend these weekly meetings.

d) Explain the point at which the experiment will terminate. If appropriate, include the standards for the termination of the participation of the individual participant Also discuss plans for ensuring necessary medical or professional intervention in the event of adverse effects to the participants.

The experiment will end at either the normal termination or whenever the subject decides to withdraw from the study. Participants will be asked to complete the brief monthly in person or telephone assessments as described in the follow-up phase. In the event that an interim analysis demonstrates futility, the PI, or Co-I determines unacceptable level of risk, regulatory agencies mandate discontinuation of the study, or a product recall occurs that necessitates stopping the study, any planned iTBS-TMS treatments will be immediately discontinued.

e) Data Safety and Monitoring Plan (DSMP). See guidance on Data Safety and Monitoring.

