All data including signed consent form documents must be retained for a minimum of three years past the completion of the research. Additional requirements may be imposed by your funding agency, your department, or other entities. (Policy on Retention of and Access to Research Data, Research Policy Handbook, <http://doeresearch.stanford.edu/policies/research-policy-handbook/conduct-research/retention-and-access-research-data>)

APPROVAL LETTER/NOTICE NOTE: List all items (verbatim) that you want to be included in your approval letter (e.g., Amendment date, Investigator's Brochure version, consent form(s) version(s), advertisement name, etc.) in the box below.

Y By checking this box, I verify that I, as the Protocol Director (PD) responsible for this research protocol, have read and agree to abide by the above obligations, or that I have been delegated authority by the PD to certify that the PD has read and agrees to abide by the above obligations.

Data Analyses

Primary Hypothesis:

1a) Veterans who receive active rTMS treatment for AUD demonstrate a significantly lower frequency of relapse at 6 months following treatment than controls (i.e., Veterans with AUD who receive sham rTMS).

Statistical Approach: Primary Hypothesis 1a will be tested with binary logistic regression. The criterion/dependent measure is relapse status (abstained or relapsed during the 6 months after last rTMS session). Treatment group (active rTMS vs. control) is the target predictor, and covariates will include age and composite neurocognitive functioning (based on demographically adjusted RBANS total score) as these variables may account for both within and between subject group variance [89, 91]. PTSD severity (based on PCL-5 total score), substance use severity (based on NIDA Drug Survey composite score), depression severity (based on BDI total score), and/or smoking severity (based on pack-years) will be considered as covariates if, after random assignment, there are post-hoc differences between treatment groups on these variables following breaking of the blind.

1b) Veterans who receive active rTMS treatment for AUD will demonstrate a significantly greater duration of abstinence in the 6 months following treatment than controls.

Statistical Approach: Primary Hypothesis 1b will be tested with Cox regression. The criterion/dependent measure is duration of abstinence after final rTMS session, and covariates include those listed for Primary Hypothesis 1a.

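### Randomised participants withdrawn for alcohol or substance use during treatment have no stated place in primary analyses 1a and 1b

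*Combined protocol and SAP*

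**What the plan says.** Section 2(a), under Design, Treatment Phase and Treatment Arms, places randomisation ahead of treatment: "After screening and baseline procedures, participants will be randomized to active or sham rTMS conditions". Section 9(c), under iTBS-TMS administration, then sets the checks for the two treatment weeks: "Participants will be randomly screened x6 for alcohol (breath alcohol) and substance use (urine toxicology) prior to rTMS sessions". Participants who test positive or "report any alcohol or substance use during the 2 week rTMS treatment period, they will be immediately withdrawn from the study".

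Three other places bear on what happens next.

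- Section 9(c), seizures: "the participant will be withdrawn from the study immediately although they will still be followed for protocol assessments".
- Section 9(c), Follow-up Phase: "If a participant discloses that they relapsed during the follow-up period, they will be encouraged to recontact VAPAHCS Addiction Treatment Services". Withdrawal is not mentioned.
- Section 9(d), on ending participation: "Participants will be asked to complete the brief monthly in person or telephone assessments as described in the follow-up phase".

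In the Data Analyses section, Primary Hypothesis 1a is a logistic regression on "relapse status (abstained or relapsed during the 6 months after last rTMS session", and 1b is a Cox regression on "duration of abstinence after final rTMS session". That section names no analysis set, no rule for missing data or censoring, and no scoring rule for withdrawn participants. It does not define relapse beyond the two categories.

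**The concern.** The trial asks whether stimulation reduces the return to drinking, and section 9(c) withdraws people for drinking. Because this happens after randomisation, leaving them out of 1a and 1b would select the analysed groups on an early form of the primary outcome, and the protection that randomisation gives would be weakened. If they stay in but their drinking falls before the last session, an early relapse goes uncounted.

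At stake is who is in both primary analyses and whether the triggering drinking is an event. Without a written rule, a reader of the results cannot tell which comparison was reported.

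**Working it through.** **Passages side by side.** The documents allow at least three treatments of the same person.

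1. *Excluded.* Withdrawal from the study is taken at face value. The seizure paragraph has an explicit follow-up clause and the alcohol and substance rule has none.
2. *Kept, triggering use counted.* Section 9(d) applies and the last session means the last one received. Screens come before sessions, so a positive screen stops the course there, and use since the previous session falls after time zero.
3. *Kept, triggering use not counted.* The use came before the last session received. This is possible because there are six screens against 20 sessions, and because use can also be self-reported later.

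**Illustration of exclusion.** There is no figure in the plan to reproduce: 100 participants are stated without effect size, significance level, power or dropout. Inputs:

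- 50 per arm (section 2(a)).
- Sham relapse P = 60%, borrowed from the background rate in section 1(b), which is given there as a minimum.
- Active relapse P = 40%, assumed.
- Proportion withdrawn q, assumed, with every withdrawn participant taken to be an alcohol relapse.
- Two-sided 5% level, assumed; no covariates.

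Formulas:

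- Relapse rate among those kept = (P − q)/(1 − q), with n = 50(1 − q).
- Odds ratio, sham to active = [(Ps − qs)/(1 − Ps)] / [(Pa − qa)/(1 − Pa)].
- Power for 1a: pooled two-proportion normal approximation.
- For 1b: exponential times, censored at 6 months; hazard ratio, active to sham = ln(1 − active rate kept)/ln(1 − sham rate kept); power from 20,000 simulated log-rank tests per row.

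Worked row, 10% sham and 4% active withdrawn. Sham: 0.50/0.90 = 55.6%, n = 45. Active: 0.36/0.96 = 37.5%, n = 48. Odds ratio: (0.50/0.40)/(0.36/0.60) = 1.25/0.60 = 2.08.

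| Withdrawn, sham/active | Relapse among kept | Difference (points) | Odds ratio | Power 1a | Hazard ratio | Power 1b |
|---|---|---|---|---|---|---|
| 0/0 | 60.0% vs 40.0% | 20.0 | 2.25 | 51.6% | 0.56 | 54% |
| 4%/2% | 58.3% vs 38.8% | 19.6 | 2.21 | 48.7% | 0.56 | 51% |
| 6%/4% | 57.4% vs 37.5% | 19.9 | 2.25 | 49.5% | 0.55 | 51% |
| 10%/4% | 55.6% vs 37.5% | 18.1 | 2.08 | 41.4% | 0.58 | 43% |
| 5%/10% | 57.9% vs 33.3% | 24.6 | 2.75 | 66.4% | 0.47 | 67% |

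The odds ratio after exclusion is the full one times (1 − qs/Ps)/(1 − qa/Pa). It therefore does not move when withdrawal is proportional to relapse, as in the 6%/4% row (0.06/0.60 = 0.04/0.40 = 0.10). Otherwise it can move either way.

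**No difference in total relapse (60% in both arms).** Withdrawal of 5%/5% rejects in about 5% of trials in both analyses; 5%/10% in 5.6% (1a) and 5.8% (1b); 5%/20% in 11.4% and 11.9%.

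**Exclusion against not counting, by counts.** Take 30/50 sham and 20/50 active relapsed (Pearson chi-square, p = 0.046), and assume those withdrawn have no further relapse recorded.

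- 5 sham and 2 active withdrawn: excluded, 25/45 vs 18/48, odds ratio 2.08, p = 0.081; kept but not counted, 25/50 vs 18/50, odds ratio 1.78, p = 0.157.
- 2 sham and 5 active withdrawn: excluded, 28/48 vs 15/45, odds ratio 2.80, p = 0.016; kept but not counted, 28/50 vs 15/50, odds ratio 2.97, p = 0.009.

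These counts start close to 0.05 by construction. They show that the rule matters with a handful of people, not that a result would flip.

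**The case against.** The best defence is that the plan does not exclude these people. The seizure paragraph uses nearly the same withdrawal wording for participants who are still followed, so the phrase alone does not mean that outcome data are lost. Section 9(d) can be read as asking everyone who stops early for the monthly contacts. On the last-session-received reading, some triggering use already counts. The different handling of drinking in follow-up is no defect in itself, since there is then no stimulation to stop. The grant application cited in section 2(a) and listed in section 16 is not in the documents and could hold an analysis set.

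Much of this stands, and it makes exclusion one plausible reading, not an established one. It does not close the gap: neither the seizure clause nor section 9(d) says how such a participant is scored, and use before the last session received stays uncounted.

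The objection to the numbers also stands in part. Participants must be abstinent for 5 days before the first session, and section (e) of Resources says most come from a residential programme with 24-hour monitoring. In the mild rows the effect estimates barely change. The 5%/10% row needs active stimulation to double in-treatment use while lowering 6-month relapse. The 11.4% figure needs in-treatment use four times as frequent on active as on sham, with identical total relapse.

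**Conclusion.** The gap is real and should be fixed: the documents combine an outcome-related withdrawal after randomisation with outcomes that start at the last session, and state no analysis set or scoring rule.

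A reader might infer more: that the plan drops these participants, that 1a and 1b are biased, or that the 5% level is inflated. The documents support none of these. Exclusion is not written. The direction of any bias depends on how withdrawal differs by arm, which is not given. If withdrawal is equal by arm under no effect, the 5% level holds.

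The size is unknown and may be negligible. The figures above rest on assumed relapse and withdrawal rates, apply to unadjusted analyses, and treat every withdrawal as alcohol relapse; withdrawals for other substances alone would mainly reduce the numbers analysed.

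**What to change.** 1. State that 1a and 1b include all randomised participants by assigned arm.
2. Score alcohol use that triggered withdrawal as relapse in 1a and as an event at the earliest time in 1b. State this as an exception to the window that starts at the last session, under a written definition of relapse. Add a sensitivity analysis with time zero at randomisation.
3. Do not count non-alcohol use alone as alcohol relapse. Use the monthly contacts where they exist; otherwise censor these participants in 1b and show 1a with them scored both ways.
4. Report withdrawals by arm and reason.
5. Reconcile the alcohol and substance rule, the seizure paragraph, section 9(d) and the Data Analyses section on follow-up after withdrawal and on the meaning of last session. The rule for stopping stimulation is not part of this change.

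If the grant application already holds such a rule, copy it into the analysis plan. Section 8(m) expected recruitment to end in September 2023 and the blind to be broken in year 6, so label the rules as set afterwards if that has happened.

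The cost is analysis-plan wording, one protocol clarification and modest extra analysis. For alcohol-triggered withdrawals no new data are needed, because the test or report is already known; for substance-only withdrawals the monthly data may not exist and may be too late to collect. The downside is slightly higher reported relapse rates and a few events outside the stated window.
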